5. GENERAL ANALYSIS METHODS

Primary Endpoint

To evaluate the primary hypothesis—that the mean difference in respiratory support-free days (RSFDs) between the two treatment groups is significantly different from zero—we will use a two-sample parametric t-test as the primary statistical test. This test is known for its robustness to violations of normality when the sample size is sufficiently large ($n > 25$), as is the case in this trial.

To support and validate the primary analysis, we will also conduct a two-sample permutation t-test. This nonparametric test requires only the assumption of exchangeability, which is satisfied in the context of a randomized controlled trial. The permutation test provides a distribution-free confirmatory approach, reinforcing the robustness of our findings.

In addition, we will apply the semiparametric efficient and robust estimation procedure proposed by Davidian et al. [7,8] to estimate the mean treatment difference in RSFDs along with a 95% confidence interval. This method adjusts for baseline covariates predictive of the outcome, thereby improving both statistical efficiency and precision relative to unadjusted comparisons or traditional ANCOVA. This analysis also accommodates missingness in the primary endpoint (excluding death) by explicitly modeling the missing data mechanism, as described in Protocol Section 6.4.1.

In addition to the primary analysis using the main intent-to-treat (ITT) population, we will conduct sensitivity analyses using the classical ITT (cITT) and two modified ITT (mITT) analysis sets to assess the robustness of results.

Secondary endpoints

For quantitative secondary endpoints, including the key secondary endpoint of ventilator-free days (VFDs), we will apply the same analytic approach as described for the primary endpoint (RSFDs), including both unadjusted and adjusted methods using the semiparametric efficient and robust procedure proposed by Davidian et al. [7, 8]. In addition, analyses will be conducted on total RSFDs without the last-off approach, to assess consistency across definitions.

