10. SECONDARY ENDPOINTS ANALYSES

Each secondary endpoint will be analyzed and summarized using appropriate statistical methods, and results will be presented by treatment group unless otherwise specified. Tables or figures will be used where appropriate.

1. Ventilator-Free Days (VFDs) defined as 28 days minus the total duration (in days) of invasive mechanical ventilation during the first 28 days post-randomization.
 - Participants who do not survive through Day 28 will be assigned 0 VFDs.
 - Participants who remain mechanically ventilated on Day 27 will be assigned 0 VFDs.
 - Participants transferred to long-term acute care hospitals (LTACHs) will be assigned 0 VFDs.
 - Participants who withdraw from the study will be considered as having missing data.Differences in VFDs between treatment arms will be analyzed using a two-sample parametric t-test. Descriptive statistics (mean, standard deviation, median, quartiles, and range) will also be presented in summary tables.
2. Total RSFDs without last-off approach defined as 28 minus the cumulative number of days on any form of respiratory support within 28 days of randomization, without the last-off rule applied. Participants who die before Day 28 will be assigned 0 RSFDs.

Differences in RSFDs between treatment arms will be analyzed using a two-sample parametric t-test. Descriptive statistics (mean, standard deviation, median, quartiles, and range) will also be presented in summary tables.

3. Mortality will be evaluated as a time-to-event outcome through 28 days and 180 (± 42 days). Analyses will mirror those described in Section 9, including Kaplan–Meier survival curves, log-rank tests, and Cox proportional hazards models (adjusted and stratified by baseline creatinine clearance). In addition, we will test for an interaction between treatment group and period (during- vs. post-treatment) to determine if treatment effects on mortality vary over time.
4. Duration of mechanical ventilation among participants who survive through Day 28, the total number of days on invasive mechanical ventilation will be calculated. Participants transferred to LTACHs will be assigned 28 days. Differences between treatment arms will be analyzed using a two-sample parametric t-test. Descriptive statistics (mean, standard deviation, median, quartiles, and range) will also be presented in summary tables.

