5. Duration of respiratory support (with Last-Off Approach) among Day 28 survivors, the number of days on any qualifying respiratory support (applying the last-off approach) will be summarized. Participants transferred to LTACHs will be assigned 28 days. Differences between treatment arms will be analyzed using a two-sample parametric t-test. Descriptive statistics (mean, standard deviation, median, quartiles, and range) will also be presented in summary tables.
6. Oxygenation ($\text{PaO}_2/\text{FiO}_2$ ratio) measured daily on study days 1–7 will be visualized using boxplots stratified by treatment arm.
7. ICU-free days, defined as 28 minus the number of days in the intensive care unit (ICU) during the first 28 days post-randomization.
 - Participants who do not survive through day 28 will be assigned zero ICU-free days.
 - Participants who remain in the ICU on day 27 will be assigned zero ICU-free days.
 - Participants who are transferred to LTACH facilities will be assigned zero ICU-free days.
 - Participants who withdraw from the study will be considered as having missing data.Differences in ICU-free days between treatment arms will be analyzed using a two-sample parametric t-test. Descriptive statistics (mean, standard deviation, median, quartiles, and range) will also be presented in summary tables.
8. CMV DNA detection in plasma and endotracheal aspirate (ETA) by day 28 (>0 IU/mL, >1000 IU/mL), defined as positive CMV PCR from ETA, plasma, or serum specimens.
The analysis will be conducted by the unblinded protocol statistician.
Differences in CMV DNA detection in plasma and endotracheal aspirate between treatment arms will be evaluated under the competing risk framework of Fine and Gray (10). Cumulative incidence estimates will be evaluated, and Gray's test p-value will be used to test the difference between arms accounting for death as competing risk.
 - This analysis will include death as a competing risk if it occurs on the same day of the last negative CMV test date.
 - Any CMV reactivation will be considered, even those which were below the level of quantification but greater than 0.
9. A comprehensive list of all reportable AEs of Grade 3 or higher by day 28 will be provided, including onset date, AE verbatim, MedDRA code, SAE/EAE, study day, severity grade, relationship to study drug, outcome, and duration days.

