We will also compare the duration of mechanical ventilation and respiratory support by day 28 among survivors between the two intervention arms. If the rate of death by day 28 differs between the two groups, then the analysis in survivors may be biased. If there is evidence for a differential death rate, then a sensitivity analysis will be conducted to evaluate how the estimated mean difference changes with a range of assumptions about the degree of possible selection bias. The sensitivity analysis method of Shepherd will be used [91], which was designed to address “truncation by death”. A mediation analysis will also be conducted to test if CMV viremia lies in the causal pathway linking the treatment (Ganciclovir) effect with the outcome (RSFDs), that is,

if CMV viremia, which is assumed to be affected by the treatment, itself affects the outcome or not.

This analysis will be conducted in four steps:

1. A regression analysis with Treatment predicting RSFDs to test for path c alone,
2. A regression analysis with Treatment predicting CMV Viremia to test for path a,
3. A regression analysis with CMV Viremia predicting RSFDs to test the significance of path b,
4. A multiple regression analysis with Treatment and CMV Viremia predicting RSFDs.

The purpose of Steps 1-3 is to establish that zero-order relationships among the variables exist. If one or more of these relationships are non-significant, it can be concluded that mediation is not likely. If there are significant relationships in Steps 1 through 3, Step 4 is conducted. In the Step 4 model, some form of mediation is supported if the effect of CMV Viremia (path b) remains significant after controlling for Treatment. If Treatment is no longer significant when CMV Viremia is controlled, the finding supports full mediation. If effect of CMV Viremia is still significant, the finding supports partial mediation. Apart from this, static respiratory system compliance (Crs) will also be used in a separate mediation analysis to understand whether any effect of Ganciclovir is exerted via pulmonary mechanisms.

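### The SAP does not carry over, or declare dropping, the protocol's truncation-by-death sensitivity analysis for the two survivor-only duration endpoints, so a mortality imbalance in either direction could bias them unchecked

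*SAP*

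**What the plan says.** Protocol 6.2.2 plans to compare both durations among day-28 survivors and sees the difficulty: "If the rate of death by day 28 differs between the two groups, then the analysis in survivors may be biased". It then makes a conditional commitment: "If there is evidence for a differential death rate, then a sensitivity analysis will be conducted to evaluate how the estimated mean difference changes" over a range of assumptions about selection. It names the method: "The sensitivity analysis method of Shepherd will be used". It does not say what counts as evidence.

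The SAP keeps the endpoints. Section 10 item 4 reads "Duration of mechanical ventilation among participants who survive through Day 28, the total number of days on invasive mechanical ventilation will be calculated", and item 5 covers "Duration of respiratory support (with Last-Off Approach) among Day 28 survivors". For each, "Differences between treatment arms will be analyzed using a two-sample parametric t-test", with descriptive statistics. SAP Section 5 adds, for quantitative secondary endpoints, that "we will apply the same analytic approach as described for the primary endpoint (RSFDs), including both unadjusted and adjusted methods using the semiparametric" method; the primary approach also includes a permutation test.

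The SAP contains no truncation-by-death analysis and no trigger for one. The method's source is still listed as reference 9, but no SAP text cites it. Section 11 does not include the analysis. Section 12, on changes from the protocol, mentions only the additional analyses of Section 11.

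**The concern.** Randomization balances the arms at baseline, not among those alive at day 28. If one arm loses more patients, and those lost would have needed long support, that arm's survivors look as if they came off support sooner, even when the drug changes nobody's duration. If an arm keeps alive patients who need long support, its survivors look worse.

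These two endpoints will be read closely. Protocol 4.5.1 accepts that the composite cannot reveal a treatment that raises mortality while shortening support in survivors, so readers will turn to mortality and survivor durations to take the composite apart. In phase 2, ventilation duration in survivors had the smallest p-value in protocol Table 2-1 (0.006). A final report written from SAP Section 10 alone would give the survivor comparison without the check that the protocol promised.

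**Working it through.** **1. Does any SAP method fill the gap?**

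- Permutation test: the SAP justifies it by exchangeability under randomization. Selecting on survival can break that.
- Semiparametric method: it adjusts for baseline covariates, and SAP Sections 5 and 8 describe it as handling missingness for reasons other than death.
- SAP Section 3.2: its general reference to imputation and sensitivity analyses concerns measurements that could not be taken, with specimen timing as the example.
- SAP Section 10 item 8: death is treated as a competing risk, but only for CMV detection.

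None is specified to address selection on survival.

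**2. The plan's own mortality figure**

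Inputs: 250 per arm, 20% control mortality, HR 0.52, two-sided 5% (SAP 2.5; protocol Table 6-3).

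- Treated mortality under proportional hazards: 1 − (1 − 0.20)^0.52 = 0.1096.
- Power = Φ[(|p1 − p2| − 1.96·SE0)/SE1], with SE0 = √(2p̄(1 − p̄)/n) and SE1 = √((p1(1 − p1) + p2(1 − p2))/n).
- Φ[(0.0904 − 1.96 × 0.0324)/0.0321] = Φ(0.84) = 80%, as stated in the plan.

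**3. Would a significance trigger fire?**

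The same formula for 20% against 25%: p̄ = 0.225, SE0 = 0.03735, SE1 = 0.03728, so Φ[(0.05 − 0.0732)/0.03728] = Φ(−0.62) = 27%. For 28% it gives 55%, and for 30%, 73%.

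**4. How large could the shift be?**

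The documents give neither arm-level deaths nor the link between death risk and duration, so both are assumed.

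- Duration: lognormal, median 6.5 days, σ = ln(12.25/3)/(2 × 0.6745) = 1.043, rounded up and capped at 28. The scale comes from phase 2 placebo survivors (Table 2-1: 6.5, IQR 3–12.25).
- Ganciclovir has no effect on anyone's duration.
- Placebo mortality 20%; 250 per arm; 2,000 simulated trials per setting.
- ρ is the correlation between latent death risk and latent log duration.

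Mean survivor difference, ganciclovir minus placebo, in days. In brackets: share of trials in which the t-test wrongly favours ganciclovir (nominal 2.5%).

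| Ganciclovir mortality | ρ = 0 | ρ = 0.3 | ρ = 0.6 | ρ = 0.9 |
|---|---|---|---|---|
| 20% | −0.03 (2.9%) | −0.04 (3.1%) | −0.02 (2.5%) | 0.00 (2.1%) |
| 25% | 0.00 (2.5%) | −0.17 (3.8%) | −0.34 (8.1%) | −0.53 (18.6%) |
| 30% | −0.03 (2.8%) | −0.32 (6.0%) | −0.63 (14.9%) | −1.02 (56.4%) |
| 35% | 0.00 (2.5%) | −0.50 (9.1%) | −0.97 (29.9%) | −1.43 (85.9%) |

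The top row and the ρ = 0 column show no bias beyond simulation noise.

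Limiting case: the extra deaths are exactly the longest-ventilated would-be survivors. At 25% mortality the share removed is (0.25 − 0.20)/0.80 = 6.25%, and the shift is −1.2 days. At 30% it is 12.5%, and −2.4 days. If ganciclovir lowered mortality, the sign reverses: +1.1 days at 15% and +2.2 days at 10%.

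Two simplifications: a survivor-based scale is applied to all patients in the simulation, and rounding up makes the simulated quartiles (4, 7, 14) slightly longer than their source.

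**The case against.** **Silence is not cancellation.** The SAP leans on the protocol in several places, Section 12 rescinds nothing, and protocol 6.2.2 still stands. This is fair. A reader might infer that the analysis has been abandoned; the documents show only that it was not carried over and that this was not declared. The uncited reference suggests an oversight.

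**The SAP offers more than a t-test.** True: Section 5 adds permutation and baseline-adjusted analyses, so it would be wrong to say that the SAP relies on a t-test alone. As step 1 shows, the additions do not address this problem.

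**The direction is unknown.** A reader might infer from the closure of enrolment that deaths were more frequent on ganciclovir, and hence that the bias would flatter the drug. SAP Section 4 gives both safety and futility as reasons, says that the interim review recommended continuing unchanged, and reports no deaths by arm. No actual bias is shown.

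**Size relative to the design effect.** A reader might scale the bias from phase 2 free days: 17.75/0.80 = 22.19 as a survivor mean, then six points of extra deaths among patients with 5, 10 or 15 free days. That gives (17.75 − 0.06 × 5)/0.74 − 22.19 = +1.4, and likewise +1.0 and +0.6, to be set against 2.74. The arithmetic is right but the comparison is not supported. It pools both arms' ventilator-free days, combines a phase 2 mean with the phase 3 mortality assumption, places every extra death among long-support patients, and uses as yardstick an effect on a composite that scores deaths as zero.

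**The protocol's analysis is conditional.** This also stands. Running it in all cases is a recommendation beyond what the protocol promised.

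**Conclusion.** The omission is a textual fact. As written, SAP Section 10 items 4 and 5 give comparisons selected on a post-randomization event, without the safeguard that the protocol attached to them.

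The size is uncertain: no shift with equal mortality or no link between death risk and duration; 0.2 to 1.4 days in the simulated settings with excess mortality; more in the limiting case. These figures rest on the assumed durations, mortality gaps and correlations, and illustrate a range rather than estimate this trial's bias.

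The consequence is limited to secondary analyses. The primary RSFD analysis, VFDs and ICU-free days score deaths as zero and do not select on survival. The survivor-only second mITT set (SAP 3.1), used for a sensitivity analysis of RSFDs, has the same weakness.

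**What to change.** - In SAP Section 10 items 4 and 5, reinstate the truncation-by-death sensitivity analysis of protocol 6.2.2 and cite reference 9 there. State the range of selection assumptions, which neither document gives, before durations by arm are examined.
- Report survivor durations beside day-28 mortality by arm. That mortality analysis is already planned; only the placement is new.
- Preferably run the analysis without a significance trigger, because evidence of differential death is undefined and a test at the 5% level would often miss an imbalance that matters. Otherwise define the trigger.
- Add a caution on selection to the survivor mITT results.
- If the omission was intended, declare and justify it in Section 12 instead.

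The cost is a few sentences, the work of choosing the range, and a small amount of extra analysis. No new data are needed.

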11. ADDITIONAL ANALYSES

Additional analyses will be specifically described in the companion document, GRAIL 3 Statistical Analysis Plan for Exploratory and Post Hoc Analyses. These analyses are outside the scope of the FSR.

1. Subgroup analyses will be conducted to explore potential treatment effects on RSFDs and mortality across the following baseline factors:
 - Study site
 - Covid-19
 - Ventilation type
 - Sex, age, race
 - Severity scores
 - Underlying conditions
 - CMV reactivation at randomization
2. To assess potential hematopoietic toxicities and their clinical relevance, we will conduct the following analyses:
 - Comparison of lymphocyte and monocyte counts between treatment arms.
 - Stratified analyses of RSFDs and mortality by baseline lymphopenia and monocytopenia severity at predefined thresholds: <1000 cells/ μ L, <500 cells/ μ L, <100 cells/ μ L
3. Ganciclovir (GCV) may cause hepatic, pancreatic, or renal toxicity in critically ill patients. Potential toxicities will be evaluated by comparing key laboratory markers between treatment arms:
 - Hepatic: alanine transaminase (ALT)
 - Pancreatic: lipase, amylase
 - Renal: cystatin C
4. Potential neurologic toxicities of Ganciclovir will be explored, including possible associations with delirium, seizure, or cerebrovascular events. The following measures will be compared between treatment arms:
 - Delirium scores
 - Incidence of seizures
 - Incidence of stroke
5. Ganciclovir exposure may increase the risk of arrhythmias in critically ill patients. Arrhythmic events will be summarized by treatment arm, and comparisons will be made to evaluate potential cardiotoxic effects of the study drug.
6. To explore potential toxicities or complications associated with Ganciclovir, clinical conditions present at or immediately prior to death will be summarized by treatment arm. Causes of death will be tabulated and compared using appropriate statistical methods (e.g., chi-square or Fisher's exact test).
7. To evaluate the immunologic effects of Ganciclovir and CMV suppression, we will assess cytokine and proteomic responses by treatment arm. For individual cytokines, peak levels and area under the curve (AUC) over the first 7 days will be compared between randomization groups, with adjustment for baseline values.
8. Ganciclovir Exposure and Pharmacokinetics (PK) analysis: Unusually high drug levels in critically ill patients may increase toxicity.

12. STATISTICAL ANALYSIS CHANGES FROM PROTOCOL

Additional analyses outlined in Section 11 will be incorporated separately in addition to the Final Study Report (FSR) statistical analysis to further investigate potential adverse outcomes associated with Ganciclovir (GCV) exposure.

1 PROTOCOL SUMMARY

Title Ganciclovir to Prevent Reactivation of Cytomegalovirus in Patients with Acute Respiratory Failure and Sepsis

Study drugs
Ganciclovir sodium: 2-amino-9-76,9-dihydro-3H-purin-6-one.
Placebo for ganciclovir: [normal saline]

Patients Immunocompetent, CMV seropositive adults hospitalized with sepsis and acute respiratory failure requiring respiratory support

Protocol Schema

Schedule of administration*			
	Day 1 through Day 5	Day 6 through Day 28 or hospital discharge, whichever occurs earlier	
Arm	N	Twice daily	Once daily
1	250	Ganciclovir 5 mg/kg intravenously	Ganciclovir 5 mg/kg intravenously
2	250	Normal saline intravenously	Normal saline intravenously
Total	500		

* “Day” on this table refers to study day. Day 1 is the first day of study drug administration.

Primary Objective To evaluate whether administration of ganciclovir increases respiratory-support-free days in immunocompetent patients with sepsis-associated acute respiratory failure.

Primary Hypotheses We hypothesize that IV ganciclovir administered early in critical illness will effectively suppress CMV reactivation in CMV seropositive adults with sepsis-associated acute respiratory failure, thereby reducing lung damage and accelerating recovery from respiratory failure by direct and indirect mechanisms, and leading to improved clinical outcomes.

Study Design	Multicenter randomized placebo-controlled double-blind trial, [randomized in blocks for balance across study sites, with interim analyses of safety].
Study Duration	180 days per patient
Trial Safety Monitoring	Safety and Protocol Adherence Review Team (see Section 14.3) Data Safety Monitoring Board (see Section 14.5)
Study drug provider	Commercially acquired
Funding Agency	U.S. National Institutes of Health (NIH) National Heart, Lung, & Blood Institute (NHLBI)
Coordinating Center	Fred Hutchinson Cancer Center (Fred Hutch)/Vaccine & Infectious Disease Division (VIDD)
Statistical and Data Management	Fred Hutchinson Cancer Center/Vaccine & Infectious Disease Division (VIDD), Statistical Center for HIV/AIDS Research & Prevention (SCHARP)
Endpoint Laboratory(ies)	[name] Lab, Fred Hutch

2 BACKGROUND

2.1 Critical illness due to sepsis

One million people per year in the US are hospitalized with sepsis and, as the population ages, its incidence is expected to increase [1]. Sepsis is considered the most expensive condition treated in US hospitals, with an overall cost to society of ~\$38 billion in 2013, and the subset with acute respiratory failure accounts for 10% of all intensive care unit (ICU) admissions [1, 2].

2.2 Acute respiratory failure

Acute respiratory failure is a common and serious complication in hospitalized patients. Sepsis, and particularly sepsis from pneumonia, accounts for 73% of patients with acute respiratory failure [3]. Among patients with sepsis, 40% develop acute respiratory failure, with mortality rates of >30% [4, 5]. Despite this burden of illness for sepsis-associated acute respiratory failure, no pharmacologic treatments have been proven effective, and care is generally supportive [6]. The proposed intervention (IV ganciclovir to prevent cytomegalovirus [CMV]-mediated exacerbation of respiratory failure), if proven effective, would be applicable to all CMV seropositive adults, who account for at least 60% of all patients with sepsis, representing a significant improvement in care for a common, deadly, and expensive health condition.

For this study, acute respiratory failure will be defined as in Section 4.1.1 of this protocol.

